11.2 POST-PROCEDURAL TESTING

- Patients will receive 7–14 day ambulatory ECG monitoring at 3 months, 6 months and 13 months post-ablation, unless the patient has an existing cardiac implantable electronic device (CIED)
- Repeat echocardiographic examination to re-assess left atrial size/remodeling at 4–6 months is recommended

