2 STUDY ENDPOINTS

2.1 PRIMARY EFFICACY ENDPOINT

- (i) To determine whether posterior left atrial wall (PLAW) isolation in conjunction with pulmonary vein isolation (PVI), as compared to PVI alone, can yield a reduction in atrial arrhythmia recurrence at 1 year in patients with persistent/long-standing persistent atrial fibrillation (AFp) undergoing catheter ablation therapy

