6 SAMPLE SIZE

We plan to enroll 200 patients in this multicenter, prospective, randomized single-blinded trial. Of these, 100 patients will be assigned the arm receiving PVI (Group 1) and 100 patients to the arm receiving PVI + PLAW isolation (Group 2). However, an interim analysis will be performed after enrolling the first 100 patients (50 patients in each arm) to assess for the primary efficacy and safety endpoints. Decisions regarding further enrollment will be made accordingly based on this interim analysis.

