11.4 MANAGEMENT OF RECURRENT ATRIAL ARRHYTHMIA(S)

- A 3-month blanking period will be used when assessing the primary efficacy endpoint
- The date of documented first recurrence of atrial arrhythmia (i.e. AF, atrial flutter, etc) will be documented even if this were to occur prior to 3 months
- The date of first arrhythmia recurrence (i.e. AF, atrial flutter, etc) after the 3-month blanking period will also be documented
- Rhythm status at the end of the study period will be documented

- Management of recurrent arrhythmia will be left to the discretion of the patient's cardiologist/cardiac electrophysiologist; management options may include: changing or resumption of AAD, cardioversion, repeat ablation, etc
- Repeat ablation procedures are permitted during the blanking period
- The ablation strategy for a repeat procedure will be left to the discretion of the primary cardiac electrophysiologist
- All findings (including the presence of PVI durability and PLAW isolation if applicable) and details of the repeat ablation strategy will be collected and examined

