12 SAFETY

As the components of this study are all within the realm of usual clinical care and common clinical practice, we do not anticipate any incremental adverse events. Patients will report symptoms/adverse events to their local site study coordinator and primary cardiac electrophysiologist during the follow-up period. The local site primary investigator will oversee the safety of the study at his/her site. All adverse events will be reported to the Principal Investigators (Drs. [name] and [name]). Adverse events will be monitored and tallied for each 10 patients enrolled in the study.

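### The exemption from ambulatory ECG covers any existing CIED, whether or not it can record atrial arrhythmia, and no device interrogation is scheduled in its place

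*Protocol*

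**What the plan says.** The primary efficacy endpoint (Protocol section 2.1) asks whether adding posterior wall isolation "can yield a reduction in atrial arrhythmia recurrence at 1 year in patients with persistent/long-standing persistent atrial fibrillation (AFp"). Section 11.2 sets the scheduled rhythm recording after discharge: "Patients will receive 7–14 day ambulatory ECG monitoring at 3 months, 6 months and 13 months post-ablation". The same sentence then makes one exception to this schedule, worded as "unless the patient has an existing cardiac implantable electronic device (CIED"). No device type, atrial lead or detection capability is attached to the exemption. Neither section 11.2 nor any other section says when a device is to be interrogated, or that its stored data stand in for the ECG. The exclusion criteria in section 5.2 do not keep CIED patients out.

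Section 11.4 applies to everyone, with or without a device: "A 3-month blanking period will be used when assessing the primary efficacy endpoint"; "The date of first arrhythmia recurrence (i.e. AF, atrial flutter, etc) after the 3-month blanking period will also be documented"; and "Rhythm status at the end of the study period will be documented". The method for that last item is not given. Section 12 adds an unscheduled route: "Patients will report symptoms/adverse events to their local site study coordinator and primary cardiac electrophysiologist during the follow-up period".

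**The concern.** CIED is a broad class. It includes single-chamber ventricular pacemakers and defibrillators, which have no atrial lead and may hold no usable record of atrial rhythm. As section 11.2 is worded, a patient with such a device meets the exemption and wears no recorder. A patient whose device does sense the atrium may have a fuller record than a 7–14 day recorder would give, but the protocol names no time at which that record must be retrieved.

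The primary outcome is thus looked for in different ways in patients without a CIED, patients with an atrial-sensing CIED, and patients with any other CIED. In the last group an asymptomatic recurrence can go unseen. Section 11.4 asks for the date of first recurrence after blanking, while section 11.2 removes the scheduled means of finding it. An analysis plan can say how missing rhythm data are handled, but it cannot supply recordings that were never made.

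**Working it through.** **No planned figure to reproduce.** Section 6 gives 200 patients ("100 patients will be assigned the arm receiving PVI (Group 1) and 100 patients to the arm receiving PVI + PLAW isolation (Group 2")) without recurrence rates, alpha or power. What follows illustrates size under stated assumptions.

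**Step 1: who is affected.** The protocol gives no CIED share. Assume that 5–20% of patients have a CIED and that 20–30% of those devices cannot record atrial arrhythmia.
- Low end: 200 × 0.05 × 0.20 = 2 patients (1%).
- High end: 200 × 0.20 × 0.30 = 12 patients (6%).

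**Step 2: effect on observed rates.** Let f be the affected share, equal in both arms, and s the proportion of their recurrences still detected. Then

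observed rate = true rate × [1 − f × (1 − s)].

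The difference between arms shrinks by the same factor. The worst case is s = 0. Assumed true rates are 45% (PVI) and 30% (PVI + posterior wall isolation).

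**Step 3: power.** With n = 100 per arm and two-sided alpha 0.05 (assumed):

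power = Φ{[d − 1.96 × √(2p̄(1 − p̄)/n)] / √([p₁(1 − p₁) + p₂(1 − p₂)]/n)},

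where d = p₁ − p₂ and p̄ is the mean of the two observed rates.

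- f = 0: p̄ = 0.375, so Φ[(0.15 − 1.96 × 0.06847)/0.06764] = Φ(0.234) = 59.2%.
- f = 6%: rates are 0.423 and 0.282 and p̄ = 0.3525, so Φ[(0.141 − 1.96 × 0.06756)/0.06682] = Φ(0.128) = 55.1%.

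| Affected share f | Observed rates, s = 0 | Difference (points) | Power, s = 0 | Power, s = 0.5 |
|---|---|---|---|---|
| 0% | 45.00% vs 30.00% | 15.00 | 59.2% | 59.2% |
| 1% | 44.55% vs 29.70% | 14.85 | 58.6% | 58.9% |
| 3% | 43.65% vs 29.10% | 14.55 | 57.2% | 58.2% |
| 5% | 42.75% vs 28.50% | 14.25 | 55.8% | 57.5% |
| 6% | 42.30% vs 28.20% | 14.10 | 55.1% | 57.2% |

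Other assumed rates give a similar loss. With s = 0 and f = 5%, 50% vs 30% goes from 82.8% to 79.5%, and 40% vs 25% from 62.1% to 58.9%.

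**Step 4: how many patients could be misread.** Only a patient who truly recurs can have a recurrence missed. Splitting the affected patients evenly by arm:
- 2 affected: 1 × 0.45 + 1 × 0.30 = 0.75 missed recurrences in the whole trial.
- 12 affected: 6 × 0.45 + 6 × 0.30 = 4.5 in the whole trial.

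Each missed recurrence moves its arm by 1/100 = 1 point, or by 1/50 = 2 points at the section 6 interim look with 50 per arm.

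**Step 5: chance imbalance.** An affected patient shifts an arm by the recurrence risk times 1 point on average, that is by 0.30 to 0.45 points. If 12 affected patients fell 8 and 4, and both arms had a true rate of 45%, the spurious difference would be (8 − 4) × 0.45 = 1.8 points.

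**The case against.** The strongest reply is that the exemption makes sense only if the device serves as the monitor, and that reading times can be set in a monitoring manual or case report form. That is a fair reading of the intent. For atrial-sensing devices it reduces the problem to an unwritten retrieval schedule. It does not help a patient whose device cannot record atrial rhythm, because the written rule withdraws the recorder from that patient too.

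Two stronger readings are tempting, and the protocol supports neither.

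- A reader might infer that patients without recordings count as recurrence-free by default. No section says so. They could equally be censored, set to missing or counted as failures, and that choice commonly sits in the SAP, which is not at hand.
- A reader might infer that these patients have no rhythm data at all. Section 11.4 still requires rhythm status at study end and the date of first recurrence for everyone, and section 12 provides for symptom reports. A recurrence still sustained at study end could be seen then. A single status of unstated method does not date a first recurrence, however, and does not reveal an asymptomatic episode that has ended.

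It is also right that the devices are in place before the procedure, so their share is balanced between arms in expectation. The rule favours neither arm systematically. The size rests on stacked assumptions and is small at the low end. These points limit the weight of the concern; they do not remove it.

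**Conclusion.** The concern holds as a gap in ascertainment. The CIED exemption does not require a device that detects atrial arrhythmia, and no interrogation is scheduled. Detection of the primary outcome therefore differs by CIED status and may miss asymptomatic recurrences in patients whose device cannot record atrial rhythm.

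The loss is about 0.7 to 4.1 power points (59.2% to 58.6–55.1%). It rests on four assumptions that the protocol neither gives nor contradicts: 1–6% affected, none of their recurrences detected, true rates of 45% vs 30%, and two-sided alpha 0.05. If half of those recurrences are still found, the loss roughly halves. The main consequence is mild dilution toward no difference, with a chance imbalance of a point or two possible at the high end. The change is still worth making, because the missing recordings cannot be recovered once follow-up is over.

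**What to change.** In section 11.2, restrict the exemption to patients whose CIED senses and stores atrial arrhythmia episodes. State that data from those devices are retrieved at 3, 6 and 13 months, the same time points as the recorder. State that patients with any other CIED wear the ambulatory recorder like everyone else.

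This changes how the outcome is recorded, not how patients are treated. It costs a few more recorders of a kind already used in the trial (2 to 12 patients under the assumptions above), plus some data retrieval that can be done at routine device checks.

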11.3 POST-PROCEDURAL MEDICATION MANAGEMENT

- AAD therapy should be discontinued within 3 months of the procedure, however deviation to this recommendation is permitted at the discretion of the patient's cardiologist/cardiac electrophysiologist

11.4 MANAGEMENT OF RECURRENT ATRIAL ARRHYTHMIA(S)

- A 3-month blanking period will be used when assessing the primary efficacy endpoint
- The date of documented first recurrence of atrial arrhythmia (i.e. AF, atrial flutter, etc) will be documented even if this were to occur prior to 3 months
- The date of first arrhythmia recurrence (i.e. AF, atrial flutter, etc) after the 3-month blanking period will also be documented
- Rhythm status at the end of the study period will be documented

- Management of recurrent arrhythmia will be left to the discretion of the patient's cardiologist/cardiac electrophysiologist; management options may include: changing or resumption of AAD, cardioversion, repeat ablation, etc
- Repeat ablation procedures are permitted during the blanking period
- The ablation strategy for a repeat procedure will be left to the discretion of the primary cardiac electrophysiologist
- All findings (including the presence of PVI durability and PLAW isolation if applicable) and details of the repeat ablation strategy will be collected and examined

12 SAFETY

As the components of this study are all within the realm of usual clinical care and common clinical practice, we do not anticipate any incremental adverse events. Patients will report symptoms/adverse events to their local site study coordinator and primary cardiac electrophysiologist during the follow-up period. The local site primary investigator will oversee the safety of the study at his/her site. All adverse events will be reported to the Principal Investigators (Drs. [name] and [name]). Adverse events will be monitored and tallied for each 10 patients enrolled in the study.

13 RISK

As the protocol described is standard to an AFp ablation procedure, the risks of the procedure are similar to that of a standard AF procedure¹⁹ and include:

Common:

- Discomfort at the site of venous access
- Groin hematoma

Uncommon:

- Cardiac Perforation requiring drainage or surgery
- Pulmonary venous stenosis/occlusion
- Thrombus formation/stroke

- Injury to adjacent structures (phrenic nerve, esophagus, lung, cardiac valves)
- Bleeding
- Congestive heart failure
- Renal dysfunction
- Vascular complications (pseudoaneurysm, AV fistula requiring surgical intervention)
- Myocardial infarction
- Transesophageal echocardiography risks include dental and esophageal injury
- Radiation burns
- Pneumonia and/or sepsis
- Anaphylaxis
- Death

14 DATA HANDLING

Information about registry patients will be kept confidential and managed according to the requirements of the United States of American Health Insurance Portability and Accountability Act of 1996 (HIPAA). Those regulations require a signed patient authorization informing the patient of the following:

1. What protected health information (PHI) will be collected from patients
2. Who will have access to that information and why
3. Who will use or disclose that information
4. The rights of a research patient to revoke their authorization for use of their PHI

In the event that a patient revokes authorization to collect or use PHI, the investigator, by regulation, retains the ability to use all information collected prior to the revocation of patient authorization. For patients that have revoked authorization to collect or use PHI, attempts should be made to obtain permission to collect at least vital status (i.e. that the patient is alive) at the end of their scheduled registry period. In order to ensure patient confidentiality, all CRFs and patient information (NavX study DVDs, and ambulatory ECG monitors, CT/MR, echocardiograms if reviewed) will be de-identified and replaced with a unique three-digit patient identifier. Information will be stored in the office of the local study coordinator which will be locked when he/she is not in the office. The research study

coordinators, principal investigator and co-investigators will be the only people with access to this data. All data will be stored without any patient information apart from the unique three digit patient identifier. There will be a code sheet that will link the de-identified data back to the subjects. This will be encrypted and password-protected. One copy will be stored in the primary investigator's computer, and another in the research coordinator's computer.

REFERENCES

